6.9. Safety Analyses

Safety measures will include AEs, severe hypoglycemia, vital signs and weight, and treatment exposure.

Continuous safety variables, as well as the change from baseline for these variables, will be analyzed either by MMRM or ANCOVA models. Categorical variables will be summarized unless otherwise specified.

6.9.1. Extent of Exposure

Duration of exposure to study drug will be summarized based upon eCRF data. The following summary statistics will be provided: n, mean, SD, median, minimum, maximum, and sum (that is, total patient-years of exposure). The number and proportion of patients falling into the following different exposure categories will also be summarized: <4 weeks (>0 and <28 days), ≥ 4 and <8 weeks (≥ 28 and <56 days), ≥ 8 and <12 weeks (≥ 56 and <84 days) and ≥ 12 weeks (≥ 84 days).

Patients who complete the study treatment period are required to complete a safety follow-up visit without study drug. The days on study after discontinuing IP, and the days on study from date of first study drug to the last study visit date up to Visit 801 will also be summarized.

6.9.2. Adverse Events

Events that are newly reported after the first dose of IP or are reported to worsen in severity from baseline will be considered treatment-emergent adverse events (TEAEs). The Medical Dictionary for Regulatory Activities (MedDRA) lowest-level term (LLT) will be used in the treatment-emergent assessment. The maximum severity for each LLT during the baseline period will be used as baseline severity.

Serious adverse events (SAEs), AEs reported as reason for discontinuation from the IP or study, and TEAEs will be summarized in tables using the MedDRA PT, sorted by decreasing frequency. Treatment-emergent adverse events will also be summarized by PT sorted by decreasing frequency within SOC for all TEAEs and by maximum severity. For events that are specific to only 1 sex, the denominator and computation of the percentage will include only participants from the given sex. The number and proportion of participants with at least 1 event for each type of event will be summarized.

6.9.3. Hypoglycemic Events

Only severe hypoglycemia will be collected as AEs and all episodes of severe hypoglycemia will be considered as SAEs. Severe hypoglycemia rates and incidence during the treatment period (Visits 4-12) will be summarized.

A listing of patients with at least 1 severe hypoglycemia reported (as SAE) after Visit 4 (including Visit 801) will be provided.

A list of MedDRA PTs will be used for the narrow search of potential severe hypoglycemia in spontaneously reported AEs. The events identified through the search strategy that are also reported as SAEs will be summarized.

6.9.4. Injection Site Reaction

Injection site reactions will be searched by MedDRA PTs from the spontaneous AE reporting of potential injection site reactions. The number and percentage of patients experiencing treatment-emergent injection site reaction AEs will be summarized.

6.9.5. Vital Signs and Other Physical Findings

Post-baseline measurements and change from baseline to post-baseline for vital signs and physical characteristics (systolic blood pressure [SBP], diastolic blood pressure [DBP], pulse rate, weight, BMI) at the scheduled visits will be summarized for patients who have both baseline and at least 1 post-baseline result.

The measurements during the treatment period (0 to 12 weeks) will be analyzed by an MMRM model with baseline value of the response variable, visit as fixed factors and patient as the random factor.

6.9.6. Patient Narratives

Patient narratives will be provided for all patients in the study who experience any of the following “notable” events:

- deaths
- SAEs
- discontinuations from study (or study drug) due to AEs
- pregnancy

A list of patients who meet the criteria for narratives will be provided.

6.10. Continuous Glucose Monitoring Analysis

6.10.1. General Considerations

The analyses described in this section will include data collected during the entire baseline period and treatment period. Percentage and duration in target range, hypoglycemia, hyperglycemia will be analyzed for baseline (Week -2-0), Visit 7 (Week 2-4), Visit 9 (Week 6-8), and Visit 12 (Week 10-12). Other CGM variables will be analyzed for baseline (Week -2-0) and Visit 12 (Week 10-12).

To ensure that the CGM outcome variables are only calculated from CGM session days with sufficient data within the 24-hour, daytime (0600 hours to midnight), or nighttime (midnight to 0600 hours) periods, the following criterion will be used to determine a valid CGM session day to be counted into the calculation for a visit: minimum number of measures per day – at least 70% of the total measures that are supposed to be obtained (i.e., 70% of the 96 measures) for the 24-hour period.

6.10.2. CGM Variable and Analysis

The meal time will be collected in the database by eCRF. All continuous variables will be analyzed using the MMRM or ANCOVA defined in Section 6.2. LS mean of the difference between baseline (Week -2-0) and Visit 12 (Week 10-12) will be presented.

Summary statistics will include the number of observations, mean, median, maximum, minimum, and SD for all continuous measures. For categorical measures, the number of observations, proportion, and frequencies will be included in summary statistics. All analyses will be performed for data collected by visit.

Definition of the derived variables is in [Appendix 1](#).

6.10.2.1. Target Glucose Range

- Percentage and Duration (in minutes) of time per day glucose values are within target range (defined as between 70 mg/dL and 180 mg/dL [3.9 and 10.0 mmol/L]) inclusive during the daytime period, nighttime period and 24-hour period.
- Percentage and Duration (in minutes) of time per day glucose values are within target range (defined as between 70 mg/dL and 140 mg/dL [3.9 and 7.7 mmol/L]) inclusive during the daytime period, nighttime period and 24-hour period.

6.10.2.2. Hypoglycemia

- Percentage and Duration (in minutes) of time per day where glucose values are within a hypoglycemic range (defined as <54 mg/dL [3.0 mmol/L]) during the daytime period, nighttime period and 24-hour period.
- Percentage and Duration (in minutes) of time per day where glucose values are within a hypoglycemic range (defined as <70 mg/dL [3.9 mmol/L]) during daytime period, nighttime period and 24 hour period.
- Percentage and Duration (in minutes) of time per day where glucose values are within a hypoglycemic range (defined as $>=54$ mg/dL [3.0 mmol/L] and <70 mg/dL [3.9 mmol/L]) during the daytime period, nighttime period and 24-hour period.

6.10.2.3. Hyperglycemia

- Percentage and Duration (in minutes) of time per day glucose values are within a hyperglycemic range (defined as >180 mg/dL [10.0 mmol/L] during daytime, nighttime and 24-hour period).
- Percentage and Duration (in minutes) of time per day glucose values are within a hyperglycemic range (defined as >180 mg/dL [10.0 mmol/L] and $<=250$ mg/dL [13.8 mmol/L]) during daytime, nighttime and 24-hour period.
- Percentage and Duration (in minutes) of time per day glucose values are within a hyperglycemic range (defined as >250 mg/dL [13.8 mmol/L]) during daytime, nighttime and 24-hour period.
- Percentage and Duration (in minutes) of time per day glucose values are within a hyperglycemic range (defined as >300 mg/dL [16.5 mmol/L]) during daytime, nighttime and 24-hour period.

6.10.2.4. Glycemic Variability

- Within-day and between-day glucose coefficient of variation during 24-hour period.
- Within-day and between-day glucose standard deviation during a 24-hour period.
- Overall glucose variability

6.10.2.5. Mean glucose

- Mean glucose value (mg/dl) during a 24-hour period

6.10.2.6. iAUC and mean postprandial sensor glucose excursions

iAUC and mean postprandial sensor glucose excursions:

- 0 to 1 hour, 0 to 2 hours, 0 to 3 hours, 0 to 4 hours relative to meal starting time at the treatment level, excluding data collected after the next meal event
- 0 to 1 hour, 0 to 2 hours, 0 to 3 hours, 0 to 4 hours relative to meal starting time by meal (breakfast, lunch, and dinner) at the treatment level, excluding data collected after the next meal event

6.10.2.7. Highest sensor glucose

Highest sensor glucose after meals:

- 0-4 hours relative to meal starting time at the treatment level, excluding data collected after the next meal event
- 0-4 hours relative to meal starting time by meal (breakfast, lunch and dinner) at the treatment level, excluding data collected after the next meal event

6.10.2.8. Target CGM glucose

- The proportion of participants with percentage of time in target CGM glucose range (70-180 mg/dL [3.9 and 10.0 mmol/L]) $>70\%$
- The proportion of participants with percentage of time in hypoglycemia (<54 mg/dL [3.0 mmol/L]) $<1\%$
- The proportion of participants with percentage of time in hyperglycemia (>250 mg/dL [13.8 mmol/L]) $<5\%$
- The proportion of participants with percentage of time in hypoglycemia (<70 mg/dL [3.9 mmol/L]) $<4\%$
- The proportion of participants with percentage of time in hyperglycemia (>180 mg/dL [10.0 mmol/L]) $<25\%$

6.10.2.9. Other CGM variables

The following standardized glucose summary figures from the ambulatory glucose profile (AGP) will be generated, based upon the observed CGM data at baseline(week -2-0) and Visit 12 (Week 10-12):

- 24-hour period at individual patient level
- 24-hour period at the treatment level

Based upon the observed CGM data and patients dose time from study diary at baseline(week -2-0) and Visit 12 (Week 10-12):

- 0-4 hours relative to meal starting time at the treatment level, excluding data collected after the next meal event
- 0-4 hours relative to meal starting time by meal (breakfast, lunch and dinner) at the treatment level, excluding data collected after the next meal event

In addition, postprandial hypoglycemia during the following time interval after each meal and overall will also be derived:

- 0 to 1 hour, 0 to 2 hours, 2 to 4 hours, 0 to 4 hours relative to meal starting time at the treatment level, excluding data collected after the next meal event
- 0 to 1 hour, 0 to 2 hours, 2 to 4 hours, 0 to 4 hours relative to meal starting time by meal (breakfast, lunch, and dinner) at the treatment level, excluding data collected after the next meal event

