Telephone visits are indicated by shaded columns. Telephone visits can become office visits if needed. Site documentation will serve as the source for telephone visits.														
Supplies and IP														
Dispense CGM system, CGM reader, and mobile device with preloaded CGM application and complete training		X												
Note: Participants may be provided additional training at visits following Visit 2 as appropriate.														
Dispense study supplies		X		X		X		X		X				
Review/discuss CGM data and hypoglycemia events			X	X	X	X	X	X	X	X	X	X	X	X
Upload CGM data to study vendor portal				X			X		X			X		X
Train on use of study paper diary for collection of insulin dose data		X												
Dispense study diary		X		X		X		X		X				
Remind participant of study diary requirements		X	X	X	X	X	X	X	X	X	X			
Collect/review study diary and transfer insulin dose data to eCRF				X			X		X			X		X
Dispense LY900014 and Basaglar®					X			X		X				
Participant returns unused study drug supplies							X		X			X		X
Return study mobile device and CGM reader												X		X
Drug accountability				X			X		X		X		X	X
Laboratory Assessments (no fasting required)														
HbA1c		X			X		X		X		X		X	X
Chemistry panel		X												
Hematology		X												
Serum pregnancy test (in WOCBP)		X												
Urine pregnancy test				X										
Note: Urine pregnancy test must be performed within 24 hours prior to IP exposure at randomization (Visit 4) and at other times at the investigator's discretion.														
Follicle-stimulating hormone test		X												

	Screen	Baseline		Treatment Period										ED
	1	2	3	4	5	6	7	8	9	10	11	12	801	
Visit Number	1	2	3	4	5	6	7	8	9	10	11	12	801	ED
Visit Window (± days)		3	3	3	3	3	3	3	3	3	3	3	3	7
Time (weeks)	-5	-4	-2	0	1	2	4	6	8	10	11	12	14	
Telephone visits are indicated by shaded columns. Telephone visits can become office visits if needed. Site documentation will serve as the source for telephone visits.														
Note: Follicle-stimulating hormone test must be performed at Visit 1 for women at least 40 years of age with an intact uterus, not on hormone therapy, and who have had cessation of menses for at least 1 year without an alternative medical cause.														
Health Outcomes Questionnaires (to be completed on paper by study participants and data will be transferred by sites to the eCRF)														
Insulin Treatment Satisfaction Questionnaire (ITSQ)		X		X								X		X

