6.6.3. Study Prandial Insulin Therapy and Titration

Participants will continue their prestudy basal and prandial insulin therapy during the baseline period from Visits 2 to 4. At Visit 4, participants will start treatment with LY900014 and will administer their first study prandial insulin dose with the next meal following Visit 4. The total daily bolus insulin dose of LY900014 may be initiated unit-for-unit.

Study prandial insulin will be administered 0 to 2 minutes prior to the start of each meal (premorning meal, premidday meal, and preevening meal). Participants should follow a general daily pattern of administering prandial insulin doses with 3 main meals per day (morning, midday, and evening). Participants may have additional bolus insulin doses, such as with a snack, if clinically indicated.

This study will use 2 possible plans for determining prandial insulin dosing including:

- Carbohydrate-counting plan: If the participant performed flexible carbohydrate counting for prandial insulin dosing (insulin to carbohydrate ratio plan) prior to study enrollment, this plan may be continued during the study. The prandial insulin dose is based on the participant's estimated carbohydrate content of the meal (such as unit insulin per grams carbohydrate).
- Fixed-dose plan: The participant is prescribed a fixed dose or dose range of insulin for each meal. The fixed dose or dose range of insulin may be individualized for each meal.

The participant should maintain the same prandial insulin dosing plan throughout the study. Correction factor (for example, 1 unit of insulin per glucose [mg/dL or mmol/L] above target goal) may be implemented with either prandial insulin dosing plan.

Prandial insulin should be titrated to reach the protocol target glucose values during the treatment period. Decreases to the prandial insulin dose may be made at any time during the study based on the judgment of the investigator (for example, in response to hypoglycemia).

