iAUC_{0-T} will be calculated as the average value of iAUC on all valid CGM days during that visit with sufficient data to calculate the iAUC_{0-T} (Section 6.10.1). For each day, iAUC_{0-T} will be calculated as the sum of areas of all individual trapezoids within the time frame according to the formula:

$$iAUC_{0-T} = \sum_{i=1}^k A_i = \sum_{i=1}^k \frac{(G_i - G_0) + (G_{i-1} - G_0)}{2} \Delta t_i$$

where A_i is area of the respective trapezoid, G_i is glucose concentration at a particular time, G_0 is the starting glucose concentration before the start of the meal, Δt is the time interval between consecutive CGM values, which should be always 15 minutes unless missing data occur, and k is the total number of intervals within the time frame 0-T, and T could be 1 hr, 2 hr, 3 hr or 4 hr. If the intermediate time points are missing, the next available time point will be used in calculating the trapezoid area. Also since it is possible that $G_i < G_0$ or $G_{i-1} < G_0$, A_i could also be negative.

G_0 , the starting glucose concentration, will be calculated as the average of the CGM values in the time window [-29, 0] mins relative to the start of the meal (at most 2 CGM values); G_k , the last glucose concentration, is defined as the CGM values in the window [0, +14] minutes relative to the last time point of the time frame. For example, to calculate iAUC_{0-2hr} after the start of breakfast, G_k will be the CGM values in the window [0, +14] minutes relative to the 2 hours after the start of breakfast. The derivation of each iAUC_{0-T} will require that G_0 and G_k values are both available and will exclude data collected after the next meal event.

Mean Sensor Glucose Excursions

Mean sensor glucose excursions 0 to T hour(s) in a valid postmeal time interval will be calculated by averaging all excursion values within the time interval 0-T, excluding data collected after the next meal event, where excursions are defined as $G_i - G_0$ as defined in iAUC.

Glucose Variability

Glycemic variability will be evaluated using the notation below:

- i represents a time point within a time period (a 24-hour period, daytime or nighttime)
- n represents the number of time points within the time period
- k represents a day within a visit
- m represents number of days CGM is performed at a visit
- $BG_{k,i}$ represents the glucose value at time point i on day k

Within-Day Variability

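### SAP 6.10.2.9 builds the meal profiles from insulin dose time, but only LY900014 has a dose-to-meal rule, so time zero can differ between baseline and Week 12

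*SAP*

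**What the plan says.** Two clock times appear in the SAP for the same purpose.

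- **SAP 6.10.2** names the first source: "The meal time will be collected in the database by eCRF".
- **SAP 6.10.2.9** names the second, as the lead-in to the meal-related profile figures: "Based upon the observed CGM data and patients dose time from study diary at baseline(week -2-0) and Visit 12 (Week 10-12". The bullets under that lead-in have a different axis: "0-4 hours relative to meal starting time at the treatment level, excluding data collected after the next meal event".
- **SAP Appendix 1** anchors the incremental AUC on the meal. The starting glucose G0 "will be calculated as the average of the CGM values in the time window [-29, 0] mins relative to the start of the meal". Dose time is not mentioned there.

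In the protocol's Schedule of Activities (1.3), the diary entries refer to insulin doses: "Train on use of study paper diary for collection of insulin dose data" and "Collect/review study diary and transfer insulin dose data to eCRF". No section describes participants noting when a meal begins.

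On the interval between injection and meal, protocol 6.6.3 gives a rule for the study insulin: "Study prandial insulin will be administered 0 to 2 minutes prior to the start of each meal". For the run-in it says "Participants will continue their prestudy basal and prandial insulin therapy during the baseline period from Visits 2 to 4". Inclusion criterion 5 says only that the bolus analog is taken at meals and gives no interval.

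**The concern.** A profile plotted from meal start but built on injection time is correct only if the two coincide. On LY900014 they should agree to within 2 minutes. At baseline nothing in the documents makes them agree, because participants keep whatever timing they used with lispro, aspart or glulisine.

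This is a single-arm, before-and-after comparison, so no control group cancels a measurement rule that works differently in the two periods. Injection timing is also one of the things that may change at Visit 4, so any artifact would coincide with the switch of insulin. If people injected well before eating at baseline, the dose-anchored baseline window would include pre-meal minutes and lose the same number at the end. The baseline excursion would look too small, and a true fall on LY900014 could be hidden or reversed.

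The profile figures are directly exposed. The other-secondary endpoints iAUC(0-1h) and iAUC(0-2h) would be exposed only if the meal time on the eCRF were itself taken from the dose entry. The primary and gated endpoints do not use meal time.

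**Working it through.** **The plan's own figure.** There is none on this point. The documents give no expected iAUC, no SD for it and no baseline dose-to-meal interval. The sample-size figures concern daytime time in range. The check is therefore an illustration under stated assumptions.

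**Inputs from the documents**
- LY900014 is dosed 0 to 2 minutes before the meal (protocol 6.6.3). I take 1 minute as typical.
- CGM readings are 15 minutes apart. G0 is the mean of readings in the 29 minutes up to time zero, and the last value Gk is the reading 0 to 14 minutes after T (SAP Appendix 1).
- iAUC(0-T) = sum of ½[(G_i − G0) + (G_{i−1} − G0)]·Δt (SAP Appendix 1).

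**Assumed inputs**
- The same meal curve in both periods: flat before the meal, then proportional to (t/tp)·exp(1 − t/tp), peaking at tp = 60, 75 or 90 minutes.
- Time zero set to the dose, L minutes before meal start. G0 is placed at time zero, and results are averaged over the 15 possible one-minute phases of the sensor clock.

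**Ratio of dose-anchored to meal-anchored iAUC (range over the three peak times)**

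| Dose relative to meal start | iAUC(0-1h) | iAUC(0-2h) |
|---|---|---|
| 1 min before | 0.979-0.983 | 0.992-0.994 |
| 2 min before | 0.958-0.965 | 0.983-0.989 |
| 10 min before | 0.787-0.813 | 0.910-0.935 |
| 15 min before | 0.680-0.714 | 0.862-0.898 |
| 10 to 20 min after | 0.87-1.10 | 0.72-1.01 |

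**Apparent change from baseline with no change in glucose** = (ratio at 1 minute before) / (ratio at the baseline interval) − 1.
- Baseline 10 minutes before, iAUC(0-1h): 0.983/0.813 − 1 = 21% (peak at 60 minutes) to 0.979/0.787 − 1 = 24% (peak at 90 minutes).
- Baseline 15 minutes before, iAUC(0-1h): 0.983/0.714 − 1 = 38% to 0.979/0.680 − 1 = 44%.
- iAUC(0-2h): 0.994/0.935 − 1 = 6% to 0.992/0.910 − 1 = 9% at 10 minutes; 0.994/0.898 − 1 = 11% to 0.992/0.862 − 1 = 15% at 15 minutes.

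Treating the first trapezoid as a full 15-minute step instead moves the iAUC(0-1h) rises to 22-26% and 39-45%.

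**Reading.** The LY900014 rule keeps the Week 12 distortion to about 4% at most, so nearly all of any artifact would come from baseline. If dosing followed the start of the meal, iAUC could move either way. With meal start as time zero in both periods, the artifact is zero.

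**The case against.** The best defence is that the plan is already anchored on the meal. Appendix 1, SAP 6.10.2.6 and SAP 6.10.2.7 all work from meal start, SAP 6.10.2 commits to collecting meal time, and dose time appears once, in a lead-in whose own bullets return to meal start. It may be meant only to help identify meals. That narrows the point but does not remove it. The sentence names dose time as the input to the figures in both periods, and two programmers could build different windows from it.

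Four stronger readings are tempting, and the documents do not support them.

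- *The iAUC endpoints are already compromised, because dose time is the only possible source of an eCRF meal time.* This is an inference from short schedule labels. Those labels do not mention dose time either, yet the SAP says the diary holds it, so they are not a full list of fields. The diary and eCRF forms are not among the documents.
- *The profiles will shift.* A shift needs baseline dosing to differ from 0 to 2 minutes before the meal. No baseline interval is documented.
- *Correction boluses will open or close meal windows.* Protocol 6.6.3 ties the correction factor to premeal glucose, that is, to a meal. A snack bolus accompanies food, so ending a window there fits the plan's truncation at the next meal.
- *The apparent rise in iAUC(0-1h) is about 50%.* Integrating the smooth curve over exactly 0 to 60 minutes gives 63-66% of the true value at 15 minutes early and 97-98% at 1 minute, hence about 1.5. The SAP's 15-minute trapezoids and its end reading beyond the hour reduce this to the figures above.

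**Conclusion.** The inconsistency is real and worth correcting. SAP 6.10.2.9 bases meal profiles on dose time, against its own axis and against SAP 6.10.2, and the interval between dose and meal is controlled in one period only. Profiles built that way can shift between baseline and Week 12 for reasons unrelated to LY900014.

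For iAUC(0-1h) and iAUC(0-2h) the concern is conditional. They are safe if the eCRF meal time is a separate record and exposed if it is the dose time under another name; the documents do not show which. The size and direction of any shift are unknown. The 21-24% and 38-44% figures for iAUC(0-1h) assume identical glucose in both periods, a peak at 60 to 90 minutes, and every participant dosing 10 or 15 minutes early at baseline. They show how sensitive the one-hour measure is to time zero and do not estimate bias in this trial. No primary or gated result depends on this.

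**What to change.** In SAP 6.10.2.9, replace the reference to diary dose time with the recorded meal start time. State that this one time zero, from one named source, serves every postprandial variable (profiles, iAUC, excursions, highest glucose, postprandial hypoglycemia) in both periods.

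Check the diary and eCRF. If they have no separate meal-start field, add one beside the dose entry for Weeks -2 to 0 and 10 to 12. Where only a dose time exists, leave that meal out of the main iAUC analysis and use it only in a sensitivity analysis. Where both times exist, report the dose-to-meal interval at baseline and at Week 12 so that readers can judge comparability.

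The cost is a few sentences in the SAP and at most one extra field. The downside is slightly more diary burden and the loss of some meals without a start time. No change to dosing is implied.
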